## 7. RESEARCH QUESTION AND OBJECTIVES

The objective of this study is to see the impact of early initiation of etanercept on patient response compared to delayed introduction of biological treatment.

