## 8. RESEARCH METHODS

### 8.1. Study Design

- **Retrospective analysis** of patients with RA that received etanercept from Baghdad teaching hospital (Rheumatology center) from 2012 until 2018 (inclusion and exclusion criteria will apply for selecting patients).
- **Primary aim:** determine the impact of early referral for management in patients with RA compared to delayed management.
- **Secondary aims:** Determine the influence of early referral on the response to biological treatment.

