### **8.6. Data Analysis**

Categorical covariates described by frequency distribution while continuous covariates expressed in terms of their mean and standard deviation or median and interquartile range as appropriate. Patients were divided according to the mean of disease duration groups (below and above mean) and unadjusted comparisons between groups of the covariates and the outcomes are evaluated using chi2 tests for categorical data, while for continuous data, we used the student's t-test for normally distributed variables and the Kruskall-Wallis test for non-parametric data.

We determined the effect of early referral on the biologic treatment response patients with RA a multivariate analysis by using a stepwise linear regression models. The response variable is defined as DAS28 and CDAI at last visit. The baseline variables considered demographic data, disease duration (years), methotrexate (yes/no), Current steroid therapy (yes/no), baseline DAS28 and CDAI, RF positive (yes/no), anti-CCP (yes/no), present smoking (yes/no).

We determined the effect of early response by using the difference between the base line DAS28 and CDAI. P value <0.05 considered statistically significant.

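### The primary aim has no adjusted analysis of its own: the one stepwise model may condition on status at etanercept start, which follows the delay under study

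*Combined protocol and SAP*

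**What the plan says.** Section 7 gives the objective as the "impact of early initiation of etanercept on patient response compared to delayed introduction of biological treatment". Section 8.1 then sets two aims. The primary aim is to "determine the impact of early referral for management in patients with RA compared to delayed management". The secondary aim is "Determine the influence of early referral on the response to biological treatment". Section 8.3 names DAS28 and CDAI at the last follow-up visit as the primary outcomes.

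Section 8.6 measures early versus late by disease duration and describes three analyses:

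- **A split at the mean of disease duration**, with "unadjusted comparisons between groups of the covariates and the outcomes are evaluated using chi2 tests for categorical data" and t or rank tests for continuous data.
- **One adjusted analysis**, "a multivariate analysis by using a stepwise linear regression models", introduced with "We determined the effect of early referral on the biologic treatment response". The response is the last-visit score. The variables considered are demographics, disease duration in years, RF, anti-CCP, smoking and "methotrexate (yes/no), Current steroid therapy (yes/no), baseline DAS28 and CDAI".
- **A loosely worded effect of early response**, based on a difference involving the baseline scores.

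No section dates baseline or current steroid use, gives stepwise entry or removal rules, or separates an overall from a direct effect of delay. Section 8.8 names only missing data as a limitation.

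**The concern.** Section 7 contrasts early with delayed introduction of treatment, so the delay ends when etanercept starts. Disease activity, steroid use and methotrexate use at that moment lie at the end of the exposure, and the delay may have changed them. A model that holds them fixed asks whether, among patients in the same state at start, longer disease goes with a worse last visit. That is a sensible question about response to the biologic. It is not the question of what early rather than delayed management does overall, because it sets aside any harm that acts by leaving patients more active or more steroid-dependent at start.

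Delayed patients could therefore start worse and end worse while the adjusted duration coefficient looks small, and a reader could take that as evidence that delay does not matter. The only alternatives offered have no confounder control.

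**Working it through.** **What can be reproduced.** The plan states no effect size, SD or power, and section 8.4 says there was no predefined study size. There is no figure to reproduce, so every number below is an assumption or follows from one.

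**Aims against analyses (sections 8.1 and 8.6)**

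| Analysis | Confounder control | Keeps the effect acting through status at start? |
|---|---|---|
| Split at mean duration | None | Yes |
| Stepwise regression | Whatever is selected | Only if the baseline variables drop out |
| Baseline difference | None | Unclear; if it is change from baseline, status at start is subtracted |

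No row combines confounder control with a reliable overall effect.

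**Path arithmetic (baseline DAS28 path only).** Let b be the change in DAS28 at start per year of delay, k the coefficient of baseline on last-visit DAS28, and c the direct effect per year. In a linear model with no unmeasured common causes:

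- overall slope = c + b×k
- slope reported with baseline in the model = c
- share removed = b×k / (c + b×k)

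Assumed values: b = 0.02, 0.04 or −0.03; k = 0.3 or 0.5; c = 0.01 or 0.02.

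| b | k | b×k | Overall, c = 0.01 | Removed | Overall, c = 0.02 | Removed |
|---|---|---|---|---|---|---|
| 0.02 | 0.3 | 0.006 | 0.016 | 38% | 0.026 | 23% |
| 0.02 | 0.5 | 0.010 | 0.020 | 50% | 0.030 | 33% |
| 0.04 | 0.3 | 0.012 | 0.022 | 55% | 0.032 | 38% |
| 0.04 | 0.5 | 0.020 | 0.030 | 67% | 0.040 | 50% |
| −0.03 | 0.3 | −0.009 | 0.001 | – | 0.011 | – |
| −0.03 | 0.5 | −0.015 | −0.005 | – | 0.005 | – |

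With positive b, the part removed over a 10-year difference is 10 × 0.006 = 0.06 to 10 × 0.020 = 0.20 DAS28 units. With negative b (early starters sicker), the overall slope is −0.005 to 0.011 while the model still reports 0.010 to 0.020. The distortion can go either way.

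**What selection does.** This was checked by simulation with 400 runs per setting and n = 150 or 500. Assumptions, with delay in SD units and residual SD 1:

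- direct effect of delay 0.15
- delay to baseline slope 0, 0.1 or 0.3; baseline to last-visit slope 0.3 or 0.5
- delay shifts the log-odds of steroid use by +0.3 and of methotrexate use by −0.3; these shift the outcome by +0.2 and −0.2
- backward elimination at p<0.05, since section 8.6 gives no other threshold

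Results:

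- The delay-only slope was about 0.17 to 0.33. With all three status variables it was 0.14 to 0.155, so 16% to 54% was lost.
- Baseline DAS28 was kept in 94% to 100% of runs.
- Steroid and methotrexate were each kept in 21% to 28% of runs at n = 150 and 57% to 67% at n = 500.
- Duration itself was dropped in 46% to 55% of runs at n = 150 and 5% to 10% at n = 500.
- In one setting with an unmeasured common cause of baseline and last-visit activity (n = 500), the delay-only slope was 0.321 and the fully adjusted slope 0.045, well below the true direct effect of 0.15.

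**Age.** Age at start = age at onset + disease duration, so age at start is itself increased by delay. If Y = βD + γ(age at start), then Y = (β + γ)D + γ(age at onset). The duration coefficient differs by γ according to which age is used, so the model must say which.

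**The case against.** The strongest reply is that the regression is introduced as an analysis of response to the biologic, close to the secondary aim, and that sections 7 and 8.2 (Hypothesis) also speak of response. For that question, adjustment for baseline activity is defensible. This stands: the model is not wrong for its stated purpose. What remains is that section 8.1 puts a different aim first and no adjusted analysis serves it.

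A reader might infer that the model always conditions on disease activity, steroid and methotrexate, so that the effect through all three is always lost. The documents do not support that. The variables are candidates in a stepwise procedure; on the assumed inputs, retention is near certain only for baseline DAS28. A reader might also infer that leaving them out gives the true overall effect. It does not. Section 8.2 says treatment decisions followed ACR recommendations, so disease activity may have prompted an earlier start and would then confound as well as mediate. The size of that confounding is unknown.

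Three further limits stand. Etanercept start as the baseline date is inferred. RF, anti-CCP and smoking are undated, so their being unaffected by delay is an assumption. The registry holds only biologic-treated patients, and at least one year of follow-up and of etanercept use is required. Both selections follow the delay, and no regression on these data undoes them.

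**Conclusion.** The concern holds in limited form. Section 8.6 contains no adjusted analysis that reliably estimates the overall association of delay with the primary outcomes. Its one adjusted model leaves to selection whether an overall or a direct effect is estimated, and whether duration is in the model at all.

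The size cannot be known from the documents. The 23% to 67% range is illustrative and covers only the baseline DAS28 path; the reversed case shows that even the direction is open. The conclusion rests on baseline meaning etanercept start, and on reading the primary aim as the overall consequence of delay, which section 8.1 implies but does not spell out. Baseline adjustment itself is not at fault and should stay for the secondary aim. The plan should be changed on this point, but the change is an added, clearly specified analysis, not a rejection of the existing one.

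**What to change.** In section 8.6, define the baseline date and replace stepwise selection with two specified models per outcome, with disease duration forced into both:

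- **Model 1 (primary aim, overall association):** last-visit score on disease duration, adjusted for age at onset (age minus disease duration), gender, education, RF, anti-CCP and smoking. Baseline DAS28/CDAI, steroid and methotrexate are left out.
- **Model 2 (secondary aim, response given status at start):** Model 1 plus the outcome's own baseline score, steroid and methotrexate.

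Report both side by side, tie each to its aim, and describe the difference as an association, not as a proven mediated effect. Section 5 says the protocol was written after the analysis was complete, so label both models post hoc.

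Add to section 8.8 that Model 1 is open to confounding by severity that prompted an early start; that Model 2 may be biased by unmeasured common causes of baseline and last-visit activity; and that both apply only to biologic-treated patients with at least one year of etanercept.

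The cost is two specified regressions per outcome in place of one stepwise run, using variables already listed in sections 8.3 and 8.6. No new data are needed.

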#### Study population

Patients included in the study if they met the American College of Rheumatology/EULAR (The European League Against Rheumatism) 2012 criteria for Rheumatoid Arthritis, with at least 1 year of follow up after starting their first biologic therapy.

Exclusion criteria: patients previously or currently treated with other biological therapies.

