### **8.2.2. Exclusion Criteria**

Patients meeting any of the following criteria will not be included in the study:

1. Had previous biological treatment.
2. Use etanercept for less than 1 year.

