### **8.3. Data Sources**

We identified patients in rheumatology registry with rheumatoid arthritis and obtained information on patient demographics (age, gender), education level (years), present smoking status, disease duration (years), current steroid therapy (yes/no), baseline DAS28 (Disease Activity Index 28) & CDAI (Clinical Disease Activity Index) RF (Rheumatoid factor) status, anticitrullinated protein antibody (anti-CCP) status. Primary Outcomes: Disease activity Index (DAS28) and CDAI in last follow up visit.

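### The 'early response' measure in section 8.6 names only baseline scores, so as written it cannot measure response; the main last-visit analysis is not affected

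*Combined protocol and SAP*

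**What the plan says.** Section 8.6 (Data Analysis) describes three pieces of analysis.

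- Unadjusted comparisons of covariates and outcomes between patients below and above the mean disease duration, by chi-squared, t or Kruskal-Wallis tests.
- For the effect of early referral, "a multivariate analysis by using a stepwise linear regression models". Here "The response variable is defined as DAS28 and CDAI at last visit", and the candidate covariates are given as: "The baseline variables considered demographic data, disease duration (years), methotrexate (yes/no), Current steroid therapy (yes/no), baseline DAS28 and CDAI", followed by serology and smoking.
- A separate sentence on early response: "We determined the effect of early response by using the difference between the base line DAS28 and CDAI". Only the significance threshold follows it.

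Section 8.3 (Data Sources) lists among the items obtained "baseline DAS28 (Disease Activity Index 28) & CDAI (Clinical Disease Activity Index"), and gives the primary outcomes as "Disease activity Index (DAS28) and CDAI in last follow up visit". No other visit is mentioned.

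Eligibility fixes the earliest possible last visit. The study population paragraph of section 8.2 requires patients "with at least 1 year of follow up after starting their first biologic therapy", and section 8.2.2 excludes those meeting the criterion "Use etanercept for less than 1 year".

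Section 5 (Milestones) records that the protocol was written after the analysis had been completed.

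**The concern.** A measure of response needs at least one value taken after treatment starts. The early-response sentence names none. Taken literally, it subtracts one baseline index from another. If that quantity differed between patients with short and long disease duration, the difference would describe the groups before etanercept and nothing else.

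If a follow-up term was simply left out, several quantities remain possible: unadjusted change, baseline-adjusted change, or change to some visit other than the last. These need not agree. The groups are formed by disease duration and not by randomisation, so baseline activity may well differ between them, and that is when unadjusted and adjusted change part company. A reader given a p-value for early response could not tell which comparison it belonged to.

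**Working it through.** The plan gives no figure to reproduce: there is no sample size, effect size or standard deviation. The check has two parts.

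**1. Can the missing term be recovered from the text?**

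- *Meaning of the baseline phrase.* In the covariate list of 8.6 and in 8.3, the word baseline followed by the two score names means the two baseline scores. The disputed sentence uses the same construction, so its wording supplies two baseline values and no later one.
- *Second time point.* The only post-baseline scores listed anywhere are those at the last visit (8.3 and 8.6). They are attached to the primary outcomes and the regression. Nothing attaches them to this difference.
- *Test or model.* The t and Kruskal-Wallis tests are assigned to covariates and outcomes, and 8.3 names only last-visit scores as outcomes. The regression is assigned to the last-visit scores. Neither is assigned to the difference.
- *The word early.* The last visit is at least 1 year after start, so it does not fit an early time point. The term 'early response' occurs once in the document; 'early referral' occurs three times (twice in 8.1, once in 8.6). A slip is possible but not established.

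**2. Does it matter which quantity was computed?**

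For one score, let B be baseline, L the last-visit value, D disease duration and X the other covariates, the same set throughout. Fit by least squares:

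- L on D, B and X: coefficient b for D and g for B.
- B on D and X: coefficient d for D.

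Define change as C = B − L. Then:

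- *Baseline-adjusted change* (C on D, B, X). Since C = −bD + (1 − g)B − (terms in X) − residual, the coefficient of D is **−b**. The residuals are those of the last-visit model with the sign reversed, so the standard error and p-value are identical.
- *Unadjusted change* (C on D, X, without B). The coefficient of D in L without B is b + gd, so in C it is d − (b + gd) = **(1 − g)d − b**.
- *Gap between the two*: **(1 − g)d**. It equals d if g = 0, and vanishes if g = 1 or d = 0.
- *Literal measure* (baseline DAS28 minus baseline CDAI). No last-visit value enters, so b does not appear. If neither baseline score is among the covariates, the coefficient is d(DAS28) − d(CDAI). That formula does not hold if the baseline scores are themselves adjusted for.

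With D as a below/above-mean indicator and no X, the same algebra covers the unadjusted group comparison; d is then the baseline difference between groups.

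An invented data set shows the pattern only (n = 120, same baseline data in each row, g = 0.416, d = 0.0777; (1 − 0.416) × 0.0777 = 0.0454):

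| True last-visit effect per year | Literal difference | Adjusted change | Unadjusted change |
|---|---|---|---|
| 0 | 0.0010 | −0.0129 | −0.0129 + 0.0454 = 0.0325 |
| 0.05 | 0.0010 | −0.0629 | −0.0629 + 0.0454 = −0.0175 |
| 0.10 | 0.0010 | −0.1129 | −0.1129 + 0.0454 = −0.0675 |

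The literal measure does not move when the true effect does. The two change measures differ by a constant 0.0454. These values were chosen for illustration and say nothing about the size in this study.

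The equality between adjusted change and the last-visit result requires D and B to be in both models. Stepwise selection guarantees neither.

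**The case against.** The strongest reply is that this is a drafting slip. Subtracting CDAI from DAS28 makes little sense, and on the scores listed the only available within-score difference is baseline versus last visit. Any reader would supply the missing words, and the analysis had already been done, so the sponsor need only say what was computed. The t and Kruskal-Wallis tests of 8.6 are also a natural candidate for comparing the difference.

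Much of that stands. Change to last visit is the likely intent, and if it was what was computed, correcting the sentence is clerical. But supplying the last visit does not say whether baseline was adjusted for or which test or model was used, and those choices can change the answer.

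A reader might also infer more than the documents support:

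- *That response is undefined throughout the plan.* It is not. Section 8.6 defines the response variable of the main regression and names the model.
- *That the secondary aim is left without an analysis.* Section 8.1 asks about the influence of early referral on response to biological treatment, and the regression in 8.6 addresses that directly. No section ties the early-response sentence to that aim.
- *That the meaningless baseline difference was in fact computed.* The wording permits this but does not show it.
- *That the reported results are biased by a known amount.* Neither g nor d is available, so no size can be claimed.

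It can also be said that retaining terms in the stepwise model goes beyond repairing one sentence. It does, but without it the relation between change and the last-visit result is not assured, and disease duration, the variable that carries early versus late referral, could be dropped by the selection.

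**Conclusion.** The point holds within a limited scope. The rule for early response, followed as written, cannot measure response to etanercept, and no section repairs it or gives it a test or model. The main last-visit analysis is defined and stands apart from it, so what is at stake is this one additional measure and any claim reported from it.

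The conclusion about the wording rests on the text alone. The algebra assumes linear regression (or a difference in means), with the same patients, visit and covariates across the models compared. How far unadjusted and adjusted change diverge here is (1 − g)d in the units of each score, possibly zero, and cannot be stated from the documents. The correction should be made before any early-response result is interpreted.

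**What to change.** 1. Replace the sentence in 8.6 with change from baseline to last visit, separately for DAS28 and for CDAI. State the direction of subtraction and the test or model and covariates actually used. If the literal baseline difference was computed, withdraw it as a response measure and label its replacement post hoc.
2. Replace the term 'early response', or define it and name the visit. As the data are listed, the only post-baseline scores are those at the last visit, 1 year or more after start.
3. In the last-visit regression, keep disease duration and the same-score baseline in the model whatever the stepwise procedure selects. Baseline-adjusted change then reproduces the duration coefficient with the sign reversed, so report it as a restatement and not as further evidence. If unadjusted change is also shown, say that in non-randomised groups it answers a different question from the adjusted coefficient.

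The cost is a few sentences, a re-run on baseline and last-visit scores already held, and one or two degrees of freedom per model. New data extraction would be needed only if a visit earlier than the last were wanted.

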### **8.7. Quality Control**

N/A.

## **8.8. Limitations of the Research Methods**

The limitation of this project could be the missing data that could lead to some bias.

## **8.9. Other Aspects**

Not Applicable (N/A).

# **9. PROTECTION OF HUMAN SUBJECTS**

## **9.1. Patient Information**

This study involves data that exist in anonymized structured format and contain no patient personal information.

## **9.2. Patient Consent**

As this study involves anonymized structured data, which according to applicable legal requirements do not contain data subject to privacy laws, obtaining informed consent from patients by Pfizer is not required.

## **9.3. Institutional Review Board (IRB)/Independent Ethics Committee (IEC)**

Not required.

## **9.4. Ethical Conduct of the Study**

The study conducted in accordance with legal and regulatory requirements, as well as with scientific purpose, value and rigor and follow generally accepted research practices described in Guidelines for Good Pharmacoepidemiology Practices (GPP) issued by the International Society for Pharmacoepidemiology (ISPE), Good Epidemiological Practice (GEP) guidelines issued by the International Epidemiological Association (IEA), and Good Practices for Outcomes Research issued by the International Society for Pharmacoeconomics and Outcomes Research (ISPOR).

# **10. MANAGEMENT AND REPORTING OF ADVERSE EVENTS/ADVERSE REACTIONS**

This study involves data that exist as structured data by the time of study start.

In these data sources, individual patient data are not retrieved or validated, and it is not possible to link (ie, identify a potential association between) a particular product and medical event for any individual. Thus, the minimum criteria for reporting an adverse event (AE) (ie, identifiable patient, identifiable reporter, a suspect product, and event) cannot be met.

